**Avapritinib**  
**Statistical Analysis Plan Study BLU-285-1303**

Descriptive statistics will be provided for the duration of treatment in weeks.

**4.5.2 Cumulative Dose**

Cumulative dose (mg) is defined as sum of all doses taken. The dosage will be counted as 0 for days when the study drug is not taken.

**4.5.3 Average Daily Dose**

Average daily dose (mg) is defined as the cumulative dose divided by the number of days dosed.

**4.5.4 Dose Intensity**

Dose intensity (mg/day) is defined as the cumulative dose divided by the duration of treatment (in days).

**4.5.5 Relative Dose Intensity**

Relative dose intensity is defined as the ratio: dose intensity / planned dose intensity. Planned dose intensity is based on initial assigned daily dose.

Relative dose intensity will be summarized both descriptively as a continuous variable and categorically in the following groups: <75%, 75% to <90%, 90% to 120%, and  $\geq 120\%$ .

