At least 70% of the patients enrolled should be receiving the study drug as their third distinct TKI treatment for GIST, ie, no more than 30% of patients should be receiving the study drug as their fourth distinct TKI treatment for GIST. In addition, patients will

receive BSC, excluding any additional anticancer therapy such as any systemic antineoplastic therapy (including kinase inhibitors and chemotherapy), radiation therapy, or surgery.

All patients will present to the study center on C1D1 for the first dose of study drug, vital sign measurements, physical exam, quality-of-life (QoL) assessment, PRO assessments, laboratory assessments, ECG and AE recording. In Cycle 2 Day 1 (C2D1), Cycle 3 Day 1 (C3D1), Cycle 4 Day 1 (C4D1) and Cycle 5 Day 1 (C5D1), patients will present to study centers for physical examination, vital signs measurements, laboratory assessments, QoL assessments, PRO assessments, ECG, and AE/concomitant medication recording. On C1D15 and C2D15, all patients will attend study center visits for vital sign measurements, serum chemistry measurements, and AE reporting. For all subsequent cycles, all patients will attend study center visits every other cycle on Day 1 of odd cycles (ie, C7D1, C9D1 etc.) for physical examination, vital sign measurements, laboratory assessments, QoL assessments, PRO assessments, ECG and AE recording. At any point in time between treatment cycles patients should attend or contact the study center for AE reporting, evaluation, and medical intervention.

[figure not shown]
Tumor assessments will be performed at Baseline and then every 8 weeks ( $\pm$  1 week) counting from C1D1, regardless of the scheduled treatment cycles, ie, if study treatment is interrupted or discontinued for any reason, tumor imaging should continue according to an 8-week schedule until tumor progression is confirmed by central radiology review. Computed tomography with intravenous (IV) contrast is the preferred imaging modality, unless a site of disease is better evaluated by MRI.

It is anticipated that patients will receive at least 1 cycle of avapritinib if randomized to Arm A and regorafenib if randomized to Arm B; no maximum treatment duration has been set. After C1, patients may continue to receive study drug until precluded by toxicity, noncompliance, pregnancy, withdrawal of consent, physician decision, PD, death, or closure of the study by the Sponsor.

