### **6.3 Dose and Administration**

Avapritinib will be administered PO at a starting dose of 300 mg QD in continuous 28-day cycles.

Prespecified dose modifications guidance for AEs related to avapritinib including cognitive effects, are described in [Section 6.3.1](#).

Regorafenib will be administered at 160 mg PO QD for 21 days in 28-day cycles with 1 week off therapy. Doses of avapritinib or regorafenib may be modified or discontinued for toxicity as described in [Section 6.3.1](#).

Patients receiving regorafenib who experience disease progression may be offered the opportunity to cross over to the avapritinib treatment arm after evaluation and confirmation of disease progression by central radiology review and a washout period of 7 to 28 days after their last dose of regorafenib; see [Section 7.6](#) for additional details. Prespecified dose modifications guidance for AEs related to regorafenib including hand-foot skin reaction, hypertension, and AST, ALT, or bilirubin increases are described in [Section 6.3.1](#).

Patients will be dispensed the appropriate number of Sponsor-packaged, labeled bottles on D1 of each cycle to allow dosing until D1 of the next cycle, which is expected to be within 28 or 56 days. Patients must return all unused tablets (or the empty bottles) at each scheduled visit.

Avapritinib doses should be administered with a glass of water (at least 8 ounces or 250 mL) in a fasted state, with no food intake from 2 hours before until 1 hour after study drug administration. Patients should be instructed to swallow tablets whole and to not chew the tablets. Antacids should not be taken within 3 hours before or after study drug administration.

Regorafenib will be provided as 40 mg strength tablets and it should be administered after a low-fat meal. See [Appendix 1](#) for additional details.

Avapritinib or regorafenib should be administered QD at approximately the same time each day. If a patient forgets to take his/her daily dose in the morning, he/she should take that dose by 4 pm that day. If the dose has not been taken by 4 pm, then that dose should be omitted, and the patient should resume treatment with the next scheduled dose.

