#### **4.5 Study Treatments and Extent of Exposure**

Study drug exposure, including the number of doses administered, cumulative dose, dose intensity, relative dose intensity (RDI), duration of treatment, and the proportion of patients with dose modifications will be summarized descriptively by time (every 4 weeks and the overall duration of the data collection period) for the Safety Population.

Day 1 + 28\*(X-1) is the start date of each 4 week period. Day 28 + 28\*(X-1) is the end date of each 4 week period. The end date of last 4 week period is the date of last dose of study drug.

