##### **4.5.1 Treatment Duration**

Duration of treatment (days) = (treatment end date – treatment start date + 1).

Duration of treatment (weeks) = (treatment end date – treatment start date + 1) / 7.

The treatment start date is the first dose date of study drug.

For patients receiving avapritinib, the treatment end date is the last dose date of study drug. For patients receiving regorafenib, the treatment end date is the earliest of the last dose date of study drug + 7 days, the data cutoff date, or the death date, to account for the dosing schedule of regorafenib.

For patients with last dose date missing, the earlier of the data cutoff date or the death date will be used.

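### SAP 4.5.5 gives regorafenib's planned dose intensity no 21/28 factor, and even at 120 mg/day two end-date rules misstate relative dose intensity for adherent control patients (minor; descriptive tables only)

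*SAP*

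**What the plan says.** Protocol 6.3 sets the control schedule: "Regorafenib will be administered at 160 mg PO QD for 21 days in 28-day cycles with 1 week off therapy". Avapritinib is taken daily without a break.

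The SAP builds RDI in steps:

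- **4.5.2 (cumulative dose):** "The dosage will be counted as 0 for days when the study drug is not taken".
- **4.5.4 (dose intensity):** cumulative dose over treatment duration in days.
- **4.5.1 (duration):** for avapritinib the end date is the last dose. For regorafenib it is the "earliest of the last dose date of study drug + 7 days, the data cutoff date, or the death date", and the SAP says the extra week is there because of the regorafenib schedule.
- **4.5.5 (RDI):** dose intensity over planned dose intensity, where "Planned dose intensity is based on initial assigned daily dose". RDI is grouped as <75%, 75% to <90%, 90% to 120%, and ≥120%.
- **4.5 (reporting):** exposure measures, including RDI, are "summarized descriptively by time (every 4 weeks and the overall duration of the data collection period) for the Safety Population". For the by-period tables, "The end date of last 4 week period is the date of last dose of study drug", with no extra week.

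**The concern.** The off week enters the regorafenib denominator at 0 mg, but the planned value it is compared with is not stated to be averaged over the schedule. Two programmers could follow this text and report 75% and 100% for the same adherent patient.

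Settling on 120 mg/day does not finish the job. The overall and by-period rules end treatment on different dates, and neither follows the schedule when a patient stops part-way through an on-period. Avapritinib has no off week, so the distortion falls on the control arm only, in tables that set the two arms' exposure side by side. Comparative safety and tolerability is a secondary objective, and these tables support how it is read.

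**Working it through.** **Inputs.** Regorafenib 160 mg on days 1–21 of 28 (Protocol 6.3). The definitions are those of SAP 4.5 to 4.5.5. Neither document gives a planned dose intensity in mg/day or an RDI value, so there is no stated figure to reproduce. Adherent means every scheduled dose is taken up to a last dose on day *d* of cycle *c* (*d* ≤ 21, written C*c*D*d*), with cutoff and death at least 7 days later.

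Doses taken: n = 21(c−1) + d. Duration under 4.5.1: T = 28(c−1) + d + 7.

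**1. Literal reading, planned = 160 mg/day.** Whole cycles: 21 × 160/28 = 120 mg/day, and 120/160 = 75.0%, exactly on a group boundary. With one missed dose:

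| Whole cycles | RDI | Scheduled doses taken |
|---|---|---|
| 1 | 20/28 = 71.4% | 20/21 = 95.2% |
| 3 | 62/84 = 73.8% | 62/63 = 98.4% |
| 6 | 125/168 = 74.4% | 125/126 = 99.2% |

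**2. Planned = 120 mg/day, overall RDI, adherent.** RDI = (n/T) × 160/120 = (n/T) × 4/3.

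| Last dose | n/T | RDI |
|---|---|---|
| C2D7 | 28/42 | 88.9% |
| C3D1 | 43/64 | 89.6% |
| C3D7 | 49/70 | 93.3% |
| C3D21 | 63/84 | 100% |
| C6D12 (day 152, about 5 months) | 117/159 | 98.1% |

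RDI is below 90% when n/T < 0.9 × 3/4 = 0.675. That holds for d ≤ 14 in cycle 1, d ≤ 8 in cycle 2 and d = 1 in cycle 3. From cycle 4 it never holds: the lowest value there is C4D1, 64/92 × 4/3 = 92.8%.

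**3. Planned = 120 mg/day, by period, adherent.** A full period gives 21 × 160/28 = 120 mg/day, so 100%. The last period ends at the last dose and gives d × 160/d = 160 mg/day, so 160/120 = 133.3% for any d from 1 to 21, in the ≥120% group. (On the literal reading the figures are 75.0% and 100%.) The periods also fail to add up to the overall duration. For a stop at C2D7 they total 28 + 7 = 35 days, against 42 under 4.5.1, so 28 × 160 = 4480 mg becomes 128.0 or 106.7 mg/day.

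**4. Edge cases at 120 mg/day.** If cutoff or death falls on the day of the last dose, the 7 days drop out and a cycle 3 stop gives 43/57 × 4/3 = 100.6% to 63/77 × 4/3 = 109.1%. If cutoff stands in for a missing last-dose date (SAP 3.2.2) and falls in the off week, the last period gives 21/22 × 4/3 = 127.3% (day 22) down to 21/28 × 4/3 = 100% (day 28).

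**5. Avapritinib.** Both rules end at the last dose and there is no off week, so an adherent patient scores 100% everywhere.

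**The case against.** **The 160 mg/day reading is uncharitable.** The SAP says the planned value is based on the assigned dose, not equal to it, and adding a week for the schedule makes sense only against a schedule average. This stands. A reader might infer that the tables will show about 75% for adherent control patients, but the documents do not establish that. They only leave the value unstated. The end-date problems in steps 2 and 3 remain at 120 mg/day.

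**Stops inside an on-period may be uncommon.** A reader might infer that the design makes them likely, because "Tumor assessments will be performed at Baseline and then every 8 weeks" and weeks 8, 16 and 24 coincide with the first day of cycles 3, 5 and 7. The documents do not support that. The scan window is ±1 week, so the week-8 scan falls on days 50–64. Days 50–56 are C2D22–28, the off week, and a patient stopped then has a last dose at C2D21 and scores 100%. Central-review turnaround is not given. An assumed PFS curve would give the share progressed by week 8, not the share with a misstated RDI.

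**Other outputs cover the gap.** At 120 mg/day an adherent stop at C2D7 and a completed second cycle after a 7-day delay (42/63 × 4/3) both score 88.9%. The dose-modification counts and listings in 4.5.6 separate those two patients, and average daily dose and compliance are unaffected. This stands and limits the harm.

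**A remedy can overshoot.** Counting each day of cycle delay as a full 160 mg day would give 42/49 = 85.7% for a 7-day delay and 42/70 = 60.0% for 28 days. An avapritinib patient losing the same time scores 56/63 = 88.9% and 56/84 = 66.7%. That would be a new bias against the control arm, so the fix must not do it.

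**Conclusion.** The point holds as a minor one. SAP 4.5.5 omits the 21/28 factor, and no constant planned value gives an adherent regorafenib patient 100% in every case. At 160 mg/day, whole cycles score 75.0%. At 120 mg/day, the last 4-week period scores 133.3%, and overall RDI is understated for stops inside an on-period: 89.6% to 100% in cycle 3, and about 2 points at C6D12, near the assumed 5-month median PFS. Under the 4.5.1 rule with 120 mg/day, an adherent patient falls below 90% only with a last dose at C1D1–14, C2D1–8 or C3D1.

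These figures assume full adherence and, unless stated, cutoff and death at least 7 days after the last dose. How many patients are affected cannot be derived from the documents. Only descriptive exposure tables change. It should not be read as a threat to any efficacy conclusion.

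**What to change.** Amend SAP 4.5 to 4.5.5 as follows.

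- State regorafenib planned dose intensity as 160 × 21/28 = 120 mg/day over whole cycles.
- Define RDI in both arms, overall and by 4-week period, as dose taken divided by dose scheduled at the initial assigned dose over the same interval, first dose to last dose. For regorafenib, schedule 160 mg on each on-day and 0 in the scheduled off week. Add no 7 days for RDI.
- Count days by which a cycle is delayed beyond 28 days at the schedule average of 120 mg/day (0.75 of a dosing day), so that a delay lowers RDI as it does for avapritinib.
- Keep dose intensity in mg/day on the 4.5.1 duration for completed cycles, adding the 7 days only when the last dose completes an on-period.
- Make the top two RDI groups non-overlapping: 90% to <120%, and ≥120%.

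Checks:

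- An adherent patient scores 100% at any stop day and in every period.
- One missed dose in six cycles: 125/126 = 99.2%.
- A 7-day delay before cycle 2: 42/(21 + 5.25 + 21) = 42/47.25 = 88.9%.
- A 28-day delay: 42/(21 + 21 + 21) = 42/63 = 66.7%. Both delay results match the avapritinib equivalents.

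The cost is one SAP definition with its delay rule, and the programming, before database lock. It uses the dosing dates already needed for cumulative dose and no new data.

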**4.5.6 Dose Modification**

The number and percentage of patients with the following dose modifications will be summarized:

- Dose reduction due to AE (0, 1, 2, or >2)
- Dose interruption/missing due to AE (0, 1, 2, or >2)
- Dose discontinuation due to AE
- Dose reduction (0, 1, 2, or >2)
- Dose interruption/missing (0, 1, 2, or >2)
- Dose discontinuation
- Dose increase (Yes, No)

Time to first dose reduction among patients with at least one dose reduction is the time elapsed, in weeks, from the date of first dose of study drug to the date when the first dose reduction occurred. Time to first dose reduction will be summarized as a continuous variable.

Details of dose modifications will be provided in listings.

#### **4.5.7 Treatment Compliance**

The number of pills dispensed, returned, and taken (defined as the difference between the number of pills dispensed and returned), and compliance (defined as the percentage of pills taken relative to pills dispensed) will be summarized descriptively for the Safety Population.

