  - c Pharmacokinetics samples will be collected before dosing (ie, predose) on Day 1 of Cycles 1, 2, 3, and 5 only from patients in Arm A of the study (those receiving avapritinib). There will be no PK samples collected from patients in Arm B of the study (those receiving regorafenib). On C3D1 and C5D1, in addition to the predose sample in all patients, samples will be collected at any 1 time point between 1-8 hours postdose. On C2D1, additional samples will be collected predose and at 1 hour ( $\pm 10$  minutes), 4 hours ( $\pm 15$  minutes), and 6-8 hours ( $\pm 15$  minutes) postdose in a total of 25 patients at selected centers. Note: The predose samples for all patients are to be collected before the day's dose of avapritinib and should be taken as close as possible to 24 hours after the prior dose was taken.
  - d Every odd Cycle D1, eg, C7D1, C9D1, etc., moving forward through EOT. Visits may be performed more frequently, if dictated by the local standard of care or if needed to adequately monitor individual patients.
  - e If an alternative antineoplastic treatment is to be started within 14 days after the last dose of study drug, the EOT visit should be conducted before the dose of alternative antineoplastic therapy. Tumor assessment for EOT procedures do not need to be repeated if they were conducted within 7 days (or within 28 days for disease response assessments).
  - f The Safety Follow-up visit may be performed by clinic visit or a phone call for resolution of any ongoing AEs.
  - g After completing the Safety Follow-up assessments, patients are to be followed for tumor imaging every 8 weeks ( $\pm 7$  days) until disease progression, death, initiation of new anti-GIST therapy, withdrawal of consent, or closure of the study by the Sponsor.
  - h After documentation of disease progression by central radiology review, patients or their designated care giver will be contacted by phone every 2 months until withdrawal of consent, death, or closure of the study by the Sponsor to collect the drug name of any new systemic antineoplastic therapy or the date of death.
  - i Patients randomized to Arm A must consent to continue avapritinib treatment after disease progression and patients randomized to Arm B must consent to cross over to avapritinib after disease progression; see [Section 7.7](#) for additional details.

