### **8.1.1 Avapritinib**

Avapritinib immediate release tablets will be supplied as 100 mg strength, round tablets composed of roller-compacted, aesthetically film-coated pharmacopeial excipients.

Avapritinib is for investigational use only and should only be used within the context of this study.

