## **8.3 Compliance**

Patients will be dispensed the appropriate number of study drug bottles to allow for dosing for a full cycle, or until the next scheduled visit. Patients are to return all unused

tablets (or the empty bottles) on D1 of each treatment cycle or at the next scheduled visit. Compliance with the dosing regimen will be assessed based on return of unused drug (or empty bottles).

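### Compliance is computed against pills dispensed, so a protocol-directed hold, dose reduction or stop within a supply interval counts as non-compliance

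*SAP*

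**What the plan says.** SAP 4.5.7 derives pills "taken (defined as the difference between the number of pills dispensed and returned" and sets "compliance (defined as the percentage of pills taken relative to pills dispensed". Both are summarized descriptively for the Safety Population. SAP 3.2.7 lists compliance among the summaries shown by treatment group.

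Protocol 8.3 states the aim: "Compliance with the dosing regimen will be assessed based on return of unused drug (or empty bottles". The same section has drug dispensed "to allow for dosing for a full cycle, or until the next scheduled visit". Protocol 6.3 puts the next visit at a point "which is expected to be within 28 or 56 days". Table 2 of the protocol has visits at each cycle through Cycle 5, and from Cycle 7 on "Every odd Cycle D1, eg, C7D1, C9D1, etc., moving forward through EOT", so supplies from Cycle 5 cover 56 days.

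Protocol 6.3.1, Table 1 and Appendix 2 direct holds (up to 56 days), dose reductions and permanent stops. SAP 4.5.7 makes no adjustment for any of these.

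**The concern.** The protocol wants adherence to the regimen. The SAP ratio reduces to 1 − returned/dispensed, which measures leftover supply. The two agree only when the instruction in force at dispensing stays in force until the supply ends. When the investigator holds the drug, lowers the dose or stops treatment partway through a supply, the tablets correctly left untaken are scored as missed.

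No other planned summary separates missed doses from directed ones. Relative dose intensity (SAP 4.5.5) is taken against the initially assigned dose, so it also falls with directed holds and reductions. The dose-modification table (SAP 4.5.6) counts interruptions and missed doses in one category. At stake is the reading of one descriptive table, shown by arm in an open-label trial of two drugs with different schedules and different dose-modification rules.

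**Working it through.** The documents state no compliance figure, so there is none to reproduce.

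**Inputs**
- Avapritinib: "starting dose of 300 mg QD in continuous 28-day cycles" (Protocol 6.3), and "Avapritinib immediate release tablets will be supplied as 100 mg strength" (Protocol 8.1.1). That is 3 tablets daily, 84 per 28 days and 168 per 56 days.
- Regorafenib: 160 mg on 21 of 28 days (Protocol 6.3) in 40 mg tablets (Protocol 8.1.2). That is 4 tablets on each dosing day, also 84 per 28 days and 168 per 56 days.
- Supplies: 28 days for Cycles 1 to 4, then 56 days (Protocol Table 2).
- Assumption: each supply holds exactly the tablets prescribed to the next visit. The documents give no bottle count; any surplus would lower the ratio further.

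**Formula:** compliance = (dispensed − returned)/dispensed. Every patient below takes every tablet prescribed.

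| Case | Avapritinib | Regorafenib |
|---|---|---|
| 7-day hold, 28-day supply | (84 − 7×3)/84 = 63/84 = 75.0% | (84 − 7×4)/84 = 56/84 = 66.7% on dosing days; 100% if it coincides with the off-week |
| 7-day hold, 56-day supply | (168 − 21)/168 = 87.5% | (168 − 28)/168 = 83.3% on dosing days |
| Reduction of one tablet, 28-day supply | after day 14: (14×3 + 14×2)/84 = 70/84 = 83.3% | after 10 dosing days: (10×4 + 11×3)/84 = 73/84 = 86.9% |
| Reduction from 3 to 2 tablets after day 14, 56-day supply | (14×3 + 42×2)/168 = 126/168 = 75.0% | – |
| Stop after day 42, whole treatment | 126/168 = 75.0% | (84 + 56)/168 = 83.3% |
| Stop 14 days after the Week 16 visit, whole treatment | (336 + 42)/504 = 75.0% | (336 + 56)/504 = 77.8% |

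With tablets prescribed as the denominator, every entry becomes 100% (63/63, 56/56, 70/70 and so on).

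**Does one arm look worse?** For a stop on day *t*, the ratio is tablets prescribed to day *t* divided by tablets supplied to the end of that supply. The effect was simulated with 400,000 patients per setting, exponential treatment durations, perfect adherence and the stop as the only deviation. As an assumption, median treatment duration was set equal to the planned PFS medians (SAP 1.3): 5 months for regorafenib and 5/0.67 = 7.46 months for avapritinib.

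| Schedule | Median (months) | Mean per patient | Pooled tablets |
|---|---|---|---|
| Regorafenib | 5 | 86.3% | 92.1% |
| Avapritinib | 7.46 | 86.1% | 93.2% |
| Avapritinib | 5 | 82.7% | 90.6% |
| Regorafenib | 7.46 | 88.9% | 94.2% |

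On the same schedule, shorter treatment gives a lower ratio: 82.7% against 86.1%, and 86.3% against 88.9%. In the actual pairing the per-patient means are nearly equal, because a regorafenib stop in the off-week returns nothing for that cycle. The pooled ratios differ by about one point in the other direction. With avapritinib kept at 7.46 months, a regorafenib median of 3 months gives 82.6% and one of 2 months gives 79.1%. A later stop can also score lower: day 152 on regorafenib gives 468/504 = 92.9%, while day 227 on avapritinib gives 681/840 = 81.1%.

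**The case against.** The strongest defence is that assessment from returned drug is what the protocol prespecifies. The SAP also reports dispensed, returned and taken counts separately, alongside dose intensity and the dose-modification tables and listings, so a reader can often see why tablets came back. The summary is descriptive. The SAP's text does not use it in any test or, by name, in the Per Protocol definition, although that definition refers to a deviations plan that is not among the documents. All of this stands and limits the consequence. It does not make the ratio a measure of adherence, because neither relative dose intensity nor the combined interruption/missing count isolates doses that the patient missed.

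A reader might infer more: that regorafenib, with the shorter expected treatment, must look less compliant by construction. The documents do not support this. At the plan's own medians the per-patient means are about equal, and the sign depends on schedule, supply length and arm-specific hold and reduction rates, which the documents do not give.

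Three related readings also go too far.
- Not every hold or reduction lowers the ratio. One set at a dispensing visit, with the supply adjusted, returns nothing; a score of 2/3 = 67% for an avapritinib reduction needs the change to come just after full-dose dispensing.
- Not every last supply is cut short. Some patients will still be on treatment at the data cutoff, and some stops fall at a visit or in the off-week.
- A stop after 14 days of a 56-day supply gives 42/168 = 25% for that interval on avapritinib but 56/168 = 33% on regorafenib, and earlier full supplies dilute either figure.

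**Conclusion.** The point holds, and it is minor. As defined, the ratio gives a wrong value for adherence whenever a directed hold, reduction or stop falls within a supply. In the worked examples fully adherent patients score between 67% and 87.5% instead of 100%. The single-supply figures are diluted when averaged over a longer treatment. The by-arm summary is distorted in a direction that cannot be stated in advance. The individual examples rest on the documents' regimens, tablet strengths and visit spacing, and on supplies that match the prescription exactly. The arm comparison rests further on treatment durations set equal to the PFS assumptions and on stops alone. The reach is one descriptive Safety Population summary; no hypothesis test, alpha or sample size is touched.

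**What to change.** In SAP 4.5.7, define compliance as pills taken divided by pills prescribed over the dosing period. Prescribed pills should be net of documented holds, dose changes, the regorafenib off-week and time after the stop date. State that a supply not yet returned at the data cutoff is left out of both numerator and denominator. If the dispensed-based ratio is also shown, label it drug accountability.

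The cost is a few lines of SAP text and one derived variable. Prescribed pills must be built from the dosing records. The SAP already relies on such records: cumulative dose (SAP 4.5.2) sums doses taken and counts untaken days as zero, and dose modifications are listed in detail (SAP 4.5.6). Protocol 10.5.4 also requires the reasons for modifications. No new data collection should be needed.
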